2.1.1.4 Unscheduled visits

Data collected at unscheduled visits will only be used in ‘by-visit’ tabulations, graphs or analyses when it can be mapped to a missed scheduled visit by the 1/3 – 2/3 rule mentioned above. If multiple unscheduled visits are allocated to the same missed scheduled visit:

- The unscheduled visit closest to the missed scheduled visit will be used;
- If there are multiple unscheduled visits with the same distance/interval to the missed scheduled visit, the latest one will be used;

To be more specific, suppose such a visit falls between two adjacent scheduled visits (e.g. visits A and B) corresponding to visit days X and Y. If the assessment day of such a visit falls within rounding ($1/3*(Y-X+1)$) after Day X, then it will be allocated to visit A, otherwise, it will be allocated to visit B. Figure 2-1 shows a graphical illustration of how this 1/3 – 2/3 rule of visit allocation is done.

Table 2-1 shows an example of the allocation of end of study/end of treatment visit to a scheduled main visit, when an assessment is scheduled to be done at every scheduled visit; and Table 2-2 shows another example of visit allocation when an assessment is only done at Baseline, Month 1 - 4, 7, 10 and 12.

All data collected at unscheduled visits will be listed.

Figure 2-1 Graphical illustration of visit allocation using the 1/3 – 2/3 rule

[figure not shown]

Table 2-1 Allocation of unscheduled visit for an assessment to be done at each scheduled visit

Scheduled main visit name/label	Scheduled visit study day	Scheduled visit window in days	Comment
Screening	-7	-7 – -1	Screening
Baseline	1	1	Baseline
W2	14	2 – 19	
M1	30	20 – 40	
M2	60	41 – 70	

M3	90	71 – 100
M4	120	101 – 130
M5	150	131 – 160
M6	180	161 – 190
M7	210	191 – 220
M8	240	221 – 250
M9	270	251 – 280
M10	300	281 – 310
M11	330	311 – 340
M12	360	>=341

Table 2-2 Allocation of unscheduled visit for an assessment to be done at Baseline, Month 1-4, 7, 10, and 12

Scheduled main visit name/label	Scheduled visit study day	Scheduled visit window in days	Comment
Baseline	1	1	Baseline
M1	30	2 – 40	
M2	60	41 – 70	
M3	90	71 – 100	
M4	120	101 – 150	
M7	210	151 – 240	
M10	300	241 – 320	
M12	360	>= 321	

2.1.1.5 Analysis periods

The on-treatment period of this study lasts from date of the first administration of study treatment to the date of the last administration of study treatment. If dates are incomplete in a way that clear assignment to pre-, on-, post-treatment period cannot be made, then the respective data will be assigned to the on-treatment period.

The post-treatment period is after the on-treatment period, which starts from 1 day after the date of the last actual administration of any study treatment until end of study (EOS).

2.1.1.6 Missing baseline and post-baseline data

Missing baseline data will not be imputed.

Observations with values ‘not done’, ‘not evaluable’, ‘not applicable’ will be treated as missing values.

2.1.1.7 Worse-seeing and better-seeing eyes

The worse-seeing eye (WSE) is defined as the eye that has the higher monocular logMAR value at baseline and the better-seeing eye (BSE) is defined as the eye that has the lower logMAR

value at baseline. For subjects with identical logMAR value of monocular DCNVA for both eyes at baseline, the right eye is defined as the worse-seeing eye.

2.1.1.8 Rule applicable to VA data collected with the digital device (M&S)

Physiologically non-plausible records

Any score of “100” for DCNVA in ETDRS letter will be considered not physiologically plausible and the value will be excluded before the analyses.

Multiple entries

If multiple entries for the same assessment are observed within one visit, the latest assessment will be used.

2.2 Analysis sets

Full Analysis Set (FAS) comprises all participants to whom study treatment has been assigned by randomization and received at least one dose of the study treatment. According to the intent to treat principle, participants will be analyzed according to the treatment and strata (if applicable) they have been assigned to during the randomization procedure. FAS will be used for all efficacy variables, unless otherwise stated.

Safety Set (SAF) includes all participants who received at least one dose of study treatment. Participants will be analyzed according to the study treatment received, where treatment received is defined as the randomized/assigned treatment, if the patient took at least one dose of that treatment, or the first treatment received if the randomized/assigned treatment was never received.

Rules of exclusion criteria of analysis sets with protocol deviations and subject classification are specified in [Section 5.5](#).

The number and percentage of subjects within each of the above analysis sets will be summarized.

2.2.1 Subgroups of interest

Subgroup analysis will be done by classifying the population according to stratification factors at randomization (See [Section 2.13](#)). In addition, analyses based on the following subgroups will be performed to assess any potential impact of the COVID-19 pandemic on key study endpoints, if there is a sufficient number of subjects in each subgroup:

- According to the internal guidance (<http://go/covid19info>), the start and end dates of the COVID-19 pandemic for different geographical regions/countries participating in Study CUNR844A2202 are defined below:

Region/Country	Start Date	End Date
Japan	21-Feb-2020	End date has not yet been defined
Rest of the World (including US, Canada, and Australia)	01-Mar-2020	End dates have not yet been defined

The following subgroups will be defined once the end dates of the regions are available:

- Exposed subjects to COVID-19 pandemic: subjects who are recruited prior to the end date;
- Non-exposed subjects to COVID-19 pandemic: subjects who are recruited on or after the end date.
- Subgroups of subjects who are infected and non-infected will be defined and identified through data in the following way:
 - Subjects infected by COVID-19: subjects who discontinue study treatment due to COVID-19 infection, or are infected by COVID-19 as identified from COVID-19 infection and health related PD term;
 - Subjects not infected by COVID-19: subjects who don't meet any of the above conditions.

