10.1 Definition of adverse events and reporting requirements

10.1.1 Adverse events

An adverse event (AE) is any untoward medical occurrence (e.g., any unfavorable and unintended sign [including abnormal laboratory findings], symptom or disease) in a clinical investigation subject after providing written informed consent for participation in the study. Therefore, an AE may or may not be temporally or causally associated with the use of a medicinal (investigational) product or an investigational device [REDACTED]

The investigator has the responsibility for managing the safety of individual subject and identifying adverse events.

Novartis qualified medical personnel will be readily available to advise on trial related medical questions or problems.

The occurrence of adverse events must be sought by non-directive questioning of the subject at each visit during the study. Adverse events also may be detected when they are volunteered by the subject during or between visits or through physical examination findings, laboratory test findings, or other assessments.

Adverse events must be recorded under the signs, symptoms, or diagnosis associated with them, accompanied by the following information (as far as possible) (if the event is serious refer to [Section 10.1.2](#)):

1. The severity grade
 - mild: usually transient in nature and generally not interfering with normal activities
 - moderate: sufficiently discomforting to interfere with normal activities
 - severe: prevents normal activities
2. Its relationship to the study treatment. If the event is due to lack of efficacy the assessment of causality will usually be 'Not suspected.' The rationale for this guidance is that the symptoms of a lack of efficacy are not caused by the trial drug, they happen in spite of its administration and/or lack of efficacy can only be evaluated meaningfully by an analysis of cohorts, not on a single subject
3. Its duration (start and end dates) or if the event is ongoing, an outcome of not recovered/not resolved must be reported
4. Whether it constitutes a SAE (see [Section 10.1.2](#) for definition of SAE) and which seriousness criteria have been met
5. Action taken regarding with study treatment. All adverse events must be treated appropriately. Treatment may include one or more of the following:
 - Dose not changed
 - Drug interrupted/withdrawn
6. Its outcome

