Supportive estimand 3:

The underlying question for the supportive estimand 3 is: what is the efficacy attributable to each UNR844 arm/dose group, after 3 months of BID treatment, taking into account any unfavorable effect of the drug such as discontinuation due to unsatisfactory therapeutic effect or Adverse Events (AE), as based on the primary estimand, assuming the subjects had no relevant intercurrent events due to COVID-19 infection. The estimand definition that addresses this question is: dose-specific difference in mean change from baseline in DCNVA at Month 3 attributable to the initially randomized medication accounting for beneficial and detrimental effect of the drug, by excluding the effect of COVID-19 infection related intercurrent events.

For this estimand, in addition to the data handling for the three types of intercurrent events, as described for the primary estimand, data following the below types of COVID-19 infection related intercurrent events will be dealt with in the following ways:

- Treatment discontinuation due to COVID-19 infection: exclude data collected post discontinuation, treat them as missing and impute assuming MAR;
- Infected by COVID-19 (identified from COVID-19 infection and health related PD term): exclude data collected post infection, treat them as missing and impute assuming MAR.

The priority rule for the primary estimand is still applicable for the supportive estimand. In addition to the priority rule for the primary estimand, if a subject has multiple intercurrent events, consider the event which occurs earliest. Data handling following this earliest intercurrent event will be according to the specifications stated above. An exception to apply only the rule of the

first intercurrent event, is when treatment discontinuation due to lack of efficacy or AEs other than COVID-19 infection (as defined by the above intercurrent events) occurs first, and infection by COVID-19 occurs later. In such a case, in order to rule out the effect due to COVID-19, while still being consistent with the primary estimand definition, both of these events need to be accounted for by applying the corresponding data handling rule following each event.

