In addition, in order to assess the impact of the COVID-19 pandemic, summary tables will be provided for the subgroups of exposed/non-exposed, infected/not-infected subjects (as defined in [Section 2.2.1](#)) by treatment, for the following safety endpoints, if there is a sufficient number of subjects in each subgroup:

[REDACTED]

For the ClinicalTrials.gov and EudraCT requirements, two tables are mandatory:

- all adverse events which are not serious adverse events with an incidence greater than X% will be provided by PT on the safety set population. Detailed threshold (X%) will be determined by safety disclosure;
- and all serious adverse events and SAE suspected to be related to study treatment will be provided by primary SOC and PT on the safety set population.

If for the same patient, several consecutive AEs (irrespective of study treatment causality, seriousness and severity) occurred with the same SOC and PT:

- a single occurrence will be counted if there is less than or equal to 1 day gap between the end date of the preceding AE and the start date of the consecutive AE;
- more than one occurrence will be counted if there is more than 1 day gap between the end date of the preceding AE and the start date of the consecutive AE.

If at least one SAE is occurring in a less than or equal 1 day gap, then one occurrence is calculated for that SAE.

The number of deaths resulting from SAEs, irrespective of study treatment relationship, will be provided by primary SOC and PT.

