5.2 AEs coding/grading

Adverse events are coded using the Medical Dictionary for Regulatory Activities (MedDRA) terminology.

The below severity grade will be used in this study:

- Mild: usually transient in nature and generally not interfering with normal activities
- Moderate: sufficiently discomforting to interfere with normal activities
- Severe: prevents normal activities

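### COVID-19 infection status ignores coded adverse events, so a participant with a COVID-19 adverse event but no COVID-19 deviation term or treatment stop is classed as not infected

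*SAP*

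**What the plan says.** SAP 2.2.1 defines the infected subgroup as participants who stop study treatment because of COVID-19 infection or "are infected by COVID-19 as identified from COVID-19 infection and health related PD term". The not-infected subgroup is the remainder: "subjects who don't meet any of the above conditions".

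SAP 2.5.3.1 adds two COVID-19 intercurrent events for supportive estimand 3, found in the same two ways. One is "Treatment discontinuation due to COVID-19 infection: exclude data collected post discontinuation". The other is "Infected by COVID-19 (identified from COVID-19 infection and health related PD term): exclude data collected post infection". In both cases the removed values are imputed as missing at random.

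The subgroup is used in two further places. SAP 2.4 plans exposure and compliance tables by infection status. The adverse event text before SAP 2.8.1.1 says that "summary tables will be provided for the subgroups of exposed/non-exposed, infected/not-infected subjects". Both refer back to 2.2.1, and both depend on there being enough participants in each subgroup.

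On adverse events, Protocol 10.1.1 states: "The occurrence of adverse events must be sought by non-directive questioning of the subject at each visit during the study". Each event is recorded with start and end dates. SAP 5.2 adds: "Adverse events are coded using the Medical Dictionary for Regulatory Activities (MedDRA) terminology".

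**The concern.** The rule relies on deviation records and treatment stops to find a medical event that the trial also collects as an adverse event. A mild infection between monthly visits, with dosing continued and no visit missed, need not lead to a treatment stop. Nothing visible in either document says that it must be entered as a deviation. Nor does any visible text say that COVID-19 adverse events are reconciled with deviation terms.

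Two things are at stake. Supportive estimand 3 is meant to remove the effect of COVID-19 infection on Month 3 DCNVA, but it would keep post-infection values from anyone the rule misses. The infected/not-infected tables would place those participants in the wrong column and make the infected column smaller. Estimand 3 also needs an infection date to decide which data come after infection, and the SAP does not say which date that is.

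**Working it through.** The plan states no figure that could be reproduced. The check is of the rule itself, followed by an illustration on assumed inputs.

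**Applying the rule.** Take a participant with a COVID-19 adverse event, no COVID-19 deviation term and no treatment stop due to COVID-19.

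1. SAP 2.2.1, first route (treatment stop): not met.
2. SAP 2.2.1, second route (deviation term): not met.
3. The participant therefore falls into the remainder and is classed as not infected.
4. SAP 2.5.3.1, supportive estimand 3: neither COVID-19 event is triggered. Post-infection DCNVA is kept unless one of the primary estimand's events applies.
5. SAP 2.4 and the adverse event text use the 2.2.1 classes, so the same label carries into those tables.

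**Does the SAP regard infection as an adverse event?** Yes. The exception rule for supportive estimand 3 speaks of discontinuation for adverse events other than COVID-19 infection. The coded adverse event data are therefore a source the SAP already recognises, but the definition does not use them.

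**Timing.** Estimand 3 concerns Month 3, so only infections up to that visit matter to it. The adverse event summaries run from first treatment to end of study. Once a participant has completed treatment, a treatment stop is no longer possible, and an infection in the treatment holiday can be found only through a deviation term.

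**Illustration.** The documents give neither an infection rate nor the share of infections that the two routes would catch. Let p be the assumed proportion infected and s the assumed share caught, with the planned N = 225 (SAP 1.1) and no one wrongly labelled infected.

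- Infected: N × p
- Missed: N × p × (1 − s)
- Share of the not-infected group that was in fact infected: p(1 − s) / (1 − p × s)

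For p = 10% and s = 0.5: infected 22.5; missed 11.25; share 11.25 / (225 − 11.25) = 5.3%.

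| p | Infected | Missed, s = 0.9 | Missed, s = 0.3 | Share, s = 0.9 | Share, s = 0.3 |
|---|---|---|---|---|---|
| 5% | 11.25 | 1.1 | 7.9 | 0.5% | 3.6% |
| 10% | 22.5 | 2.25 | 15.75 | 1.1% | 7.2% |
| 20% | 45 | 4.5 | 31.5 | 2.4% | 14.9% |
| 30% | 67.5 | 6.75 | 47.25 | 4.1% | 23.1% |

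With s = 1 every entry for missed and share is zero. The table shows how the result depends on p and s. It is not an estimate for this trial.

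**The case against.** The best defence is that the deviation category may be the infection record. Its name refers to infection and health, not to missed visits, so sites may have been told to enter every infection there. Neither document contains a list of deviation terms, so this cannot be ruled out. It stands as a limit on size: the gap may be empty. It does not make the rule sound as written, because no visible text states such an instruction or a reconciliation step.

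The defence can also say that estimand 3 concerns relevant intercurrent events, and that a mild infection with dosing continued is the least likely to be relevant. This has some force. However, SAP 2.5.3.1 lists infection as an event in its own right, with no severity condition and separately from stopping treatment.

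A reader might infer four stronger things that the documents do not support:

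- That the adverse event page is a complete record of infections. Questioning is non-directive and the visible assessment schedule has no COVID-19 test, so asymptomatic cases can be missed. It is an additional source, not a complete one.
- That COVID-19 will appear as a preferred term inside the not-infected safety tables. The list of endpoints for those tables is redacted, so their content is unknown.
- That under-counting will stop the tables from being produced. The SAP gives no threshold for a sufficient number.
- That the primary result is biased. Infection status does not enter the primary estimand, its two sensitivity analyses or the MCP-Mod test.

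Finally, the trial was stopped for lack of efficacy and the analyses were simplified (SAP 1.1 and 4), so little now depends on this subgroup. That is fair, and it is why the point is minor.

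**Conclusion.** The point holds as a minor defect in a classification rule. Under SAP 2.2.1 and 2.5.3.1 as written, a coded COVID-19 adverse event alone does not make a participant infected, and such a participant's later DCNVA remains in supportive estimand 3 unless another intercurrent event applies. How many participants this concerns cannot be obtained from the documents, and zero is possible. The effect is confined to supportive estimand 3 and the infected/not-infected tables. The conclusion rests on the visible text: parts of the SAP are redacted, but every visible use of infection status either refers to 2.2.1 or repeats its two routes.

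**What to change.** In SAP 2.2.1 and in supportive estimand 3, add a third route: an adverse event coded to a fixed list of MedDRA COVID-19 infection terms, with a start date on or after first study treatment. Not infected is then everyone who meets none of the three routes. Define the infection date as the earliest qualifying date after first dose, using the adverse event start date where there is one.

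The first-dose limit is needed because Protocol 10.1.1 counts adverse events from informed consent. Without it, a run-in infection would become an intercurrent event before treatment and would remove all post-baseline DCNVA. The Protocol glossary places intercurrent events after treatment initiation.

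Apply the revised definition to the final infected/not-infected tables. For estimand 3 the timing is different. SAP 1 says that the interim analysis is also the final analysis of the Month 3 endpoints and was completed on 24 August 2022. SAP 2.14.5.4 gives the independent statistician and programmer unmasked codes for it. Any estimand 3 re-run should therefore be reported as an additional analysis, labelled as defined after the interim, beside the result already obtained.

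The cost is a change of SAP wording, a term list and one derivation from data already collected, plus the re-run if it is wanted. The drawback is that estimand 3 would replace some observed values after mild infections with missing-at-random imputations.

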2.3 Patient disposition, demographics and other baseline characteristics

2.3.1 Subject disposition

Subject disposition will be summarized separately by treatment group and total for the FAS. Specifically, the number and proportion of subjects who discontinued the study will be summarized by treatment and total. The primary reason for premature study discontinuation will be summarized in the table.

In addition, protocol deviations (PDs) will be summarized through presenting the number and percentage of subjects with each deviation.

2.3.2 Subject demographics and other baseline characteristics

Demographic (including age, sex, race, ethnicity) and other baseline data including baseline characteristics (DCNVA, [REDACTED] cycloplegic refraction) will be listed and summarized descriptively by treatment group for the FAS.

Relevant medical histories and current medical conditions at baseline will be summarized by primary system organ class (SOC) and preferred term (PT), by treatment group separately for ocular and non-ocular histories/conditions. This includes any abnormalities noted during baseline evaluation of anterior and posterior eye segment health.

2.4 Treatments (study treatment, concomitant therapies, compliance)

The SAF will be used for the analyses below.

The duration of exposure in days to UNR844, placebo will be summarized by means of descriptive statistics using the SAF. The duration of exposure in days to UNR844 or placebo is defined as the date of the last administration of different doses of UNR844 or placebo (from

‘Study treatment’ CRF), and date of the first administration of different doses of UNR844 or placebo (from ‘Study treatment’ CRF) + 1.

Moreover, the on-treatment period (corresponding to the safety observation period) will also be summarized descriptively. The definition of the on-treatment period can be found from [Section 2.1.1.5](#).

Compliance will be presented by summarizing the total number of days with the use of study treatment twice, once, or none, and the total number of times of using study treatment by treatment group and by eye. This information will be obtained from the CRF by counting the number of days with the use of study treatment twice, once, or none in each eye. The total number of times of using study treatment will be to count all the recorded use of study treatment at the subject level for each eye during the treatment phase.

The reason for premature discontinuation of study treatment will also be summarized.

In addition, to assess any potential impact of the COVID-19 pandemic on study treatment compliance, summary tables on the duration of exposure, and the total number of days with the use of study treatment twice, once, or none, will be provided for the subgroups of exposed/non-exposed, and infected/not infected subjects, as defined in [Section 2.2.1](#), if there is a sufficient number of subjects in each subgroup.

